1.2. Study Design

Study V25L-002 is a multicenter, evaluator-blind, randomized, parallel-group, controlled study of the safety and effectiveness of JUVÉDERM VOLUX™ XC injectable gel for jawline restoration. Jawline restoration of each side of the jawline (left and right) will be assessed independently by an EI from cropped 2D [REDACTED] profile images using the ALJDS, an assessment of loss of jawline definition measured by a 5-point scale (0=None to 4=Extreme). Participants randomized to JUVÉDERM VOLUX™ XC will receive injectable gel (initial treatment) to restore jawline definition, provide a smooth contour, and achieve an aesthetically pleasing result. A touch-up treatment, if needed, will be given 30 days after initial treatment with an optional maintenance treatment available 12 months after the last treatment (initial or touch-up) received. At the initial and touch-up (if performed) treatments, the TI will determine the appropriate volume to inject to achieve at least a 1-grade improvement on the ALJDS based on clinical experience, but the maximum volume will not exceed 8.0 mL for initial and touch-up treatments combined. Injection volume for the maintenance treatment will not exceed 8.0 mL.

The following treatment groups are defined for this study:

- ! VOLUX: JUVÉDERM VOLUX™ XC injectable gel
- ! Control: No-treatment Control

Up to 20 investigational sites will enroll up to 280 participants and follow participants who meet the study criteria. Each site will have a blinded EI and a principal investigator who is responsible for the overall conduct of the study at that site and may also be the TI. The TI performs all study treatments, and the blinded EI evaluates ALJDS, GAIS, and facial sensation measurements.

The study design is presented in [Figure 1-1](#). The study will span a total of approximately 26 months: an estimated 6 months for recruitment and 20 months for follow-up. Up to

CONFIDENTIAL

JUVÉDERM VOLUX™ XC

[figure not shown]
Statistical Analysis Plan V25L-002

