The primary effectiveness variable is restoration of jawline definition based on the ALJDS evaluated by EIs. The primary effectiveness endpoint is the proportion of ALJDS responders at Month 6. A responder is defined as a participant who shows at least a 1-point improvement from baseline (pretreatment) on the ALJDS on both sides of the jaw.

Month 6 refers to 6 months after the last treatment (initial or touch-up) for participants in the treatment group and 6 months after randomization for participants in the control group.

The study device will be determined to be clinically effective if at least 50% of participants in the treatment group are observed to be responders on ALJDS at Month 6 and if the responder rate for the treatment group is statistically superior to the responder rater for the control group at Month 6. The following hypotheses will be tested:

$$H_0: P_v < 50\%$$

$$H_a: P_v \geq 50\%$$

and

$$H_0: P_v \leq P_c$$

$$H_a: P_v > P_c$$

where P_v and P_c denote the responder rates for the treatment group at Month 6 after the last treatment (initial or touch-up) and for the control group at Month 6 after randomization, respectively.

The primary effectiveness analysis will be performed based the mITT population using multiple imputation as described in Section 5.3.2. Missing values will be imputed using multiple imputation method. The pooled responder rates and 2-sided 95% CI for the responder rates in the treatment group and in the control group respectively, the pooled between-group difference in the responder rate and the corresponding 2-sided p-value will be calculated, by pooling the results from the 30 imputed data sets using PROC MIANALYZE with normal approximation in SAS.

The first hypothesis will be tested using the pooled 2-sided 95% CI for the responder rate in the treatment group. The null hypothesis will be rejected if the lower bound of the 95% CI is greater than or equal to 50%.

The second hypothesis will be tested using the pooled between-group difference in the responder rate and the corresponding p-value for the between-group difference. The null hypothesis will be

CONFIDENTIAL

Statistical Analysis Plan V25L-002

JUVÉDERM VOLUX™ XC

rejected if the 2-sided p-value is < 0.05 and the responder rate is greater for the treatment group than the control group.

In addition, the 95% CI on the proportion of responders based on the pooled estimate from the 30 imputed data sets will be provided for each treatment group.

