3. Sample Size Determination

Sample size is determined to provide adequate power to demonstrate that the product is effective as well as safe. A sample size of 120 participants in the treatment group and 40 participants in the control group will provide > 99% power to detect a difference of at least 40% in the responder rates between the 2 groups. This calculation is based on a 1-sided Fisher's exact test at the 2.5% level. The treatment group is assumed to have at least an 80% responder rate and the control group is assumed to have at most a 40% responder rate. Assuming a screen fail rate of 25% and a drop-out rate of 15% between randomization and the Month 6 visit, up to 280 participants will be enrolled, with at least 144 participants and at most 162 participants randomized to the treatment group and at least 48 participants and at most 54 participants randomized to the control group (3:1 ratio).

This sample size is considered adequate to determine the safety profile of the product in the jawline area. Assuming a screen fail rate of 25%, a 5% drop-out rate between randomization and initial treatment for the treatment group, and a 15% drop-out rate between randomization and optional treatment for the control group, it is estimated that at least 176 subjects will be treated in the study. With 176 treated subjects, there is at least 92% power to detect an AE related to treatment with an incidence rate of 1.5% in the population using a 1-sided exact binomial test at the 2.5% level.

The commercial software, PASS (2008, Version 8.0.13), was used for the power calculation. The sample size calculation used an inequality test for 2 proportions to demonstrate that the treatment group is superior to the control group. The safety calculation used an inequality test for 1 proportion.

4. Populations for Analysis

The 5 analysis populations will consist of participants as defined in [Table 4-1](#).

Table 4-1 Analysis Populations

Population	Definition	Study Treatment Assignment
mITT	All randomized participants with non-missing baseline on the ALJDS scale on both sides of the jaw	As randomized
Observed Primary Endpoint	All mITT participants who have Month 6 assessment on the ALJDS scale on both sides of the jaw	As randomized
Safety	All randomized participants who receive study treatment (VOLUX or control)	As treated ^a

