5.3.2. Main Analytical Approach

Two hypotheses regarding the proportion of ALJDS responders at Month 6 based on EI's assessment will be tested.

$$1) H_0: P_v < 50\%$$

$$H_a: P_v \geq 50\%$$

$$2) H_0: P_v \leq P_c$$

$$H_a: P_v > P_c$$

P_v denotes the responder rate for the treatment group at Month 6 after the preceding treatment and P_c denotes the responder rate for the control group at Month 6 after randomization.

The 2 hypotheses will be tested using the multiple imputation method as follows:

Step 1: The missing data will be imputed by each side of the jaw and treatment group using the fully conditional specification method with seed = 3575309 and nimpute = 30 based on the following model:

$$\text{Month 6 ALJDS} = \beta_0 + \beta_1 \text{Baseline ALJDS} + \beta_2 \text{Month 1 ALJDS} + \beta_3 \text{Month 3 ALJDS}$$

Step 2: After imputation, the changes from baseline will be calculated, from which the responder status in ALJDS at Month 6 of CP will be determined.

Step 3: Each complete dataset obtained from Steps 1 and 2 will be analyzed using SAS procedure FREQ

Step 4: The pooled results will be obtained using PROC MIANALYZE using normal approximation

The number and proportion of participants who achieved at least 1-point improvement from baseline at Month 6 during CP will be tabulated by treatment group. The pooled responder rates by treatment group and the associated p-value and 95% CI estimates based on the normal approximation will be presented. For the first hypothesis, the null hypothesis will be rejected if the lower bound of the 95% CI on the responder rate at Month 6 for VOLUX is greater than or equal to 50%. For the second hypothesis, if the 2-sided p-value is less than 0.05, then the ALJDS responder rate at Month 6 in JUVÉDERM VOLUX XC is statistically significantly different

[figure not shown]
CONFIDENTIAL

[figure not shown]
JUVÉDERM VOLUX™ XC

Statistical Analysis Plan V25L-002

from that in the no-treatment control group during the control period. Furthermore, if the responder rate is greater for JUVÉDERM VOLUX XC than the no-treatment control group, then VOLUX will be considered superior to the no-treatment control group.

The detailed SAS codes are as follows:

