5.3.3. Sensitivity Analyses

Two sensitivity analyses of the primary effectiveness endpoint will also be performed based on the mITT population.

A summary of sensitivity analyses is presented in [Table 5-3](#).

Table 5-3 Missing Data Handling Rules for the Sensitivity Analyses of the Primary Endpoint

Endpoint	Sensitivity Analysis No.	Missing Data Handling Rule	Population	Methodology
ALJDS responder rate at Month 6	1	Use observed data only	Observed Primary Endpoint	Fisher's exact test
ALJDS responder rate at Month 6	2	Multiple Imputation	mITT excluding participants who were inadvertently unblinded to the EI or who did not have a baseline ALJDS score of 2 or 3	Multiple Imputation

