6.2. Appendix 2: List of Changes

6.2.1. Changes to Protocol-Planned Analyses

The following changes to the analyses specified in the statistical sections of Study V25L-002 Amendment 2 (Approved version dated 11-March-2019) have been implemented in this SAP:

1. Four analysis populations [mITT, Safety, Observed Primary Endpoint, VT and VMT] are defined instead of the 2 analysis populations (ITT and Safety) stated in the protocol [Section 4. Populations for Analysis].
2. The primary effectiveness endpoint will be analyzed using the mITT population instead of the ITT population as stated in the protocol [Section 5.3 Primary Effectiveness Endpoint Analysis].
3. Multiple imputation will be used as the primary method for the analysis of the primary endpoint instead of using the last observation carried forward. More specifically, multiple imputation with 30 imputed datasets will be applied to participants with missing Month 6 ALJDS values, generated using the following model (performed by treatment group) [Section 5.3 Primary Effectiveness Endpoint Analysis]:

$$\text{Month 6 ALJDS} = \beta_0 + \beta_1 \text{Baseline ALJDS} + \beta_2 \text{Month 1 ALJDS} + \beta_3 \text{Month 3 ALJDS}$$

4. The analysis of the effectiveness and/or safety variables will be summarized by the VT and VMT populations in TP and MP, respectively. In CP, the analysis of the effectiveness and/or safety variables will be summarized by the mITT and Safety populations [Section 5.3.4 Supplementary Analyses and 5.6.3 Adverse Events].
5. Baseline for the primary effectiveness endpoint is defined as the last non-missing value on or before the latter of randomization date or first treatment date in the control period [Section 5.1 General Considerations]. In the protocol, Baseline is defined as the last assessment by EI prior to randomization.

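### As written, the Month 6 ALJDS imputation handles the two sides of the jaw separately, so the imputed both-sides response rate is too low in each arm

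*SAP*

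**What the plan says.** SAP 5.3.2 sets out the primary analysis in four steps. Step 1 reads: "The missing data will be imputed by each side of the jaw and treatment group using the fully conditional specification method". Its equation has three predictors: Baseline, Month 1 and Month 3 ALJDS. Step 2 derives responder status from the imputed scores, and Steps 3 and 4 analyse and pool the 30 data sets.

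SAP Section 2 defines a responder by "at least a 1-point improvement from baseline (pretreatment) on the ALJDS on both sides of the jaw". SAP 1.2 adds: "Jawline restoration of each side of the jawline (left and right) will be assessed independently by an EI". That describes separate ratings of the two sides; it does not say that the ratings are uncorrelated.

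SAP 6.2.1 item 3 restates the same equation, but describes the imputations as "generated using the following model (performed by treatment group", with no mention of a split by side. No section adds an opposite-side term, imputes the two sides jointly, or imputes participant-level status. SAP 5.3.2 announces SAS code, but the code does not appear in the text available.

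Table 5-3 lists two sensitivity analyses. The first has the rule "Use observed data only" with Fisher's exact test. The second uses multiple imputation again, on a reduced set of participants, with no different model stated.

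**The concern.** If each side is drawn separately, the imputed chance that both sides improve is the product of two one-side chances. The two sides belong to one person, with one treatment course and one visit, and usually one evaluator (Protocol 6.2 recommends the same EI throughout). Their Month 6 results are therefore likely to stay positively correlated after same-side history is taken into account. The product is then smaller than the true joint probability.

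Both primary tests rest on these imputed values, and so do the pooled rates and intervals to be reported. Raising the number of imputations reduces simulation noise but not this shift. Against the 50% threshold, the shift works against the device. In the comparison with control it favours the device at the planned rates, because the control rate falls further than the treatment rate.

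Protocol 8.3.1 planned last observation carried forward, which keeps a person's two sides together. The link was lost when the SAP made multiple imputation the primary method.

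**Working it through.** **1. The plan's own figure.** SAP Section 3 assumes 80% versus 40% responders, 120 versus 40 participants, a 1-sided Fisher test at 2.5% and 15% drop-out. Exact enumeration gives 99.4% power, which agrees with the stated figure of more than 99%. Inflating for drop-out gives 120/0.85 = 141.2, so 142, and 40/0.85 = 47.1, so 48. At 3:1, 3 × 48 = 144, which matches the stated minimum of 144 and 48.

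**2. Formula.** Let J be the true both-sides rate. Let pL and pR be the probabilities that the left and right side improve, each given its own history only.

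- Imputed rate under the written model = average of pL × pR
- Shortfall among imputed participants = J − average(pL × pR)
- Shift in the arm rate = 0.15 × shortfall

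The shortfall is zero if the sides are uncorrelated given same-side history, and positive if they are positively correlated.

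**3. No Month 1 or Month 3 data** (bivariate normal; q is the one-side rate that gives J at the assumed correlation).

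| J | Correlation | q | q² | J − q² | × 0.15 |
|---|---|---|---|---|---|
| 80% | 0.7 | 0.866 | 0.750 | 0.050 | 0.75 points |
| 80% | 0.9 | 0.843 | 0.710 | 0.090 | 1.34 points |
| 40% | 0.7 | 0.526 | 0.277 | 0.123 | 1.85 points |
| 40% | 0.9 | 0.472 | 0.222 | 0.178 | 2.66 points |

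The difference is overstated by 1.85 − 0.75 = 1.1 to 2.66 − 1.34 = 1.3 points.

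**4. Month 1 and Month 3 observed.** This uses a latent normal model with 1,000,000 simulated people per setting, conditioning on same-side Month 1 and Month 3 response. The assumed between-side correlation is 0.7 to 0.9 and the within-side visit correlation 0.5 to 0.8.

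| True rate | Shortfall among imputed | × 0.15 |
|---|---|---|
| 80% (treatment) | 2.9 to 7.8 points | 0.4 to 1.2 points |
| 40% (control) | 6.3 to 14.6 points | 0.9 to 2.2 points |

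The difference is overstated by 0.5 to 1.0 points.

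**5. Other control rates.** The plan says only that "the control group is assumed to have at most a 40% responder rate". Keeping treatment at 80%, the shift in the difference across the same settings is:

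- control 20%: +0.3 to +0.6 points
- control 10%: −0.1 to +0.2 points
- control 5%: −0.1 to −0.6 points

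**6. Weaker dependence.** With between-side correlations of 0.3, 0.6 and 0.85 and within-side visit correlations of 0.6, 0.7 and 0.65, the shifts are 0.2, 0.4 and 0.9 points (treatment) and 0.5, 0.9 and 1.7 points (control). The difference is then overstated by about 0.3 to 0.8 points. With no between-side correlation the shift is zero.

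**7. Finite samples.** Two simulations used 144 and 48 participants.

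- In one (15% missing, augmented logistic draws, 500 runs, three correlation settings), by-side minus joint imputation was −0.2 to −0.8 points (treatment) and −0.9 to −1.8 (control). That puts 0.7 to 1.0 points of the difference down to the by-side split. Joint imputation itself left −0.6 to −0.7 (treatment) and 0 to −0.2 (control). Imputing both-sides status directly (300 runs) left −0.2 to −0.4 and +0.1 to +0.7.
- In the other, by-side imputation was off by −1.0 to −1.4 (treatment) and −1.9 to −2.2 (control), a difference error of +0.7 to +0.9. Joint imputation left −0.6 to −0.7 and −0.5 to −0.7, a difference error within about 0.1 point.

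**8. Effect on the tests.** At 80% and n = 144, the lower 95% bound is 0.80 − 1.96 × √(0.80 × 0.20/144) = 0.735, far above 0.50. Normal-approximation power at 144 and 48 is 99.9% for the comparison and above 99.9% for the 50% test, with or without the shift.

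**The case against.** The strongest reply has five parts.

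- **The operative code is not visible.** SAP 6.2.2 item 2 confirms that PROC MI code exists, and it may already link the sides. This stands, and it limits the point to the written model. The text would still need correcting to match the code.
- **The correlation is assumed, and the size may be overstated.** This stands in part. Weaker dependence gives smaller shifts (step 6). The written model uses ALJDS grades and baseline rather than binary history; with four change categories as an illustration, the shortfall at 80% and 40% fell by about 6 to 19%. Neither change reverses the direction in either arm.
- **The remedy may not improve the difference.** In the first simulation of step 7, the residual errors after joint imputation combine to about −0.4 to −0.7 points in the difference, against roughly 0 to +0.6 for by-side imputation. These figures combine unpaired ranges, with no simulation error given. The second simulation compares both methods with the truth and does not bear the objection out: the error in the difference drops from +0.7 to +0.9 to about 0.1. Joint imputation does not remove the downward error in the individual arms completely.
- **No decision changes, and an observed-data analysis is planned.** Both statements are true. The observed-data test could expose the artefact, but it does not correct the primary estimate.
- **Item 3 of 6.2.1 is only a summary.** Brevity may explain its wording, but the two statements of the primary model should still agree on whether side is a split.

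**Conclusion.** The concern holds for the model as written. Under the planning rates and 15% missing, with Month 1 and Month 3 observed, the treatment rate is understated by 0.4 to 1.2 points and the control rate by 0.9 to 2.2 points. The difference is overstated by 0.5 to 1.0 points. With no post-baseline data these become 0.7 to 1.3, 1.8 to 2.7 and 1.1 to 1.3 points.

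The direction in each arm rests on a positive left-right correlation given same-side history. That is very plausible, but the documents do not give it. The direction for the difference depends on the control rate: overstated at 20 to 40%, about neutral near 10%, understated near 5%. Power and the likely outcome of both tests are essentially unaffected. The error is small, but it lies in the primary estimates and is avoidable, so it should be corrected. Confidence is medium because the code cannot be seen.

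**What to change.** In SAP 5.3.2 Step 1 and SAP 6.2.1 item 3, specify one record per participant, imputed by treatment group only. Left and right Baseline, Month 1, Month 3 and Month 6 ALJDS should all enter one fully conditional specification model. Derive both-sides responder status after imputation.

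The drawback is more correlated predictors in a control arm of 48 to 54, which the augmented-likelihood option does not cure. The SAP should therefore prespecify a fallback if the model is unstable: impute both-sides responder status directly from both sides' earlier scores. That leaves a small error of its own, as step 7 of the working shows.

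If the SAS code already includes the opposite side, only the written model in the two places needs correcting. The cost is one sentence in each place and, if the code follows the text, a small change to the imputation step. No new data are needed.

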5.7. Other Analyses

5.7.1. Subgroup analyses

Analysis of the primary effectiveness endpoint, ALJDS responder status at Month 6, will be performed on the mITT population during the CP for the following subgroups:

- ! Investigational sites by treatment group.
- ! Total volume injected (total injection volume at initial and touch-up treatments combined): \leq median and $>$ median. This analysis will be done for treatment group only.
- ! Route of injection (ie, needle or cannula). The primary effectiveness endpoint at Month 6 will be presented by route of injection (i.e., needle or cannula). A participant is defined to be in the needle group if only needle is used at both initial and touch-up treatments. A participant is defined to be in the cannula group if either only cannula is used or cannula in combination with needle at either initial or touch-up treatments. A homogeneity test will be done to compare the primary effectiveness endpoint at Month 6 between the needle and cannula groups at alpha = 0.15. This analysis will be done only for the treatment group.

! Baseline ALJDS score. If the baseline ALJDS score is different for the left and right jaws then the worse score is used as baseline score.

No multiplicity adjustment will be performed.

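### The treatment-control comparison of responder rates is not adjusted for baseline ALJDS grade, which the plan already holds for everyone analysed; adjusting would add a little precision and protect against chance imbalance.

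*SAP*

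**What the plan says.** SAP Section 2 states the test of superiority: "The second hypothesis will be tested using the pooled between-group difference in the responder rate and the corresponding p-value for the between-group difference". Its null hypothesis is "rejected if the 2-sided p-value is < 0.05 and the responder rate is greater for the treatment group than the control group". SAP 5.3.2 gives the mechanics. Missing scores are imputed (Step 1), responder status is derived (Step 2), "Each complete dataset obtained from Steps 1 and 2 will be analyzed using SAS procedure FREQ" (Step 3), and "The pooled results will be obtained using PROC MIANALYZE using normal approximation" (Step 4).

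No stratum or covariate is named in Steps 3 and 4, or for either sensitivity analysis in SAP Table 5-3. Protocol 10.1.3 describes a central 3:1 schedule and mentions no stratification factor.

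Baseline ALJDS is used in four places:

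- in deriving responder status (SAP 5.3.1);
- as a covariate in the imputation model, fitted by side and group (SAP 5.3.2, Step 1);
- in the baseline table, by jaw and by subject (SAP 6.3.2);
- as a subgroup factor (SAP 5.7.1), where the subject-level rule is "If the baseline ALJDS score is different for the left and right jaws then the worse score is used as baseline score".

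The mITT definition in SAP Table 4-1 requires a baseline score on both sides of the jaw.

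**The concern.** The endpoint is a gain of at least one grade from baseline on both sides, so the starting grade is a natural candidate for predicting response. Eligible participants start at grade 2 or 3 on each side. With about 50 controls and no stated stratification, the arms can differ by chance in their share of grade 3.

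If grade predicts response, such a difference moves the estimated effect, and the plan names no analysis that corrects for it. An adjustment added after the baseline table has been seen would be post hoc. The information needed is already collected, complete in mITT and reduced to one grade per participant. What is at stake is the width of the interval and the credibility of the estimate if the arms turn out unbalanced.

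**Working it through.** **1. The plan's own figure.** SAP Section 3 states: "A sample size of 120 participants in the treatment group and 40 participants in the control group will provide > 99% power". It adds: "This calculation is based on a 1-sided Fisher's exact test at the 2.5% level". The assumed rates are 80% (treatment) and 40% (control). Exact enumeration of the one-sided Fisher test at 120 v 40 gives 99.4%; a pooled z-test gives 99.7%. The stated power reproduces. Inflating for 15% drop-out gives 120/0.85 = 141.2, so 142, and 40/0.85 = 47.1, so 48. The planned minimum is 144 and 48.

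**2. Assumptions.** The documents give neither the grade mix nor response rates by grade. I assume half the participants at each grade, overall rates of 80% and 40%, 144 v 48 analysed, and a gap g in response between grades that is the same in both arms. I vary g from 0 to 30 points.

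**3. Chance imbalance.** SD of the between-arm difference in grade mix = sqrt(0.25/144 + 0.25/48) = 0.083, or 8.3 points. With g = 20 points, imbalance shifts the estimated effect by up to 0.083 × 0.20 × 1.96 = 0.033, or 3.3 points either way, in 95% of trials. At 120 v 40 the SD is sqrt(0.25/120 + 0.25/40) = 9.1 points, and an imbalance above 10 points has a probability of about 27%.

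**4. Variance of the difference, large-sample formula.**

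- Unadjusted: 0.8 × 0.2/144 + 0.4 × 0.6/48 = 0.00111 + 0.00500 = 0.00611. The 95% half-width is 1.96 × sqrt(0.00611) = 15.3 points.
- Part removed by stratifying: (g/2)² × (1/144 + 1/48) = (g/2)² × 0.02778.
- g = 10 points: 0.0025 × 0.02778 = 0.000069, or 1.1% of 0.00611.
- g = 20 points: 0.01 × 0.02778 = 0.000278, or 4.5%.
- g = 30 points: 0.0225 × 0.02778 = 0.000625, or 10.2%.

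**5. The same by simulation of the Mantel-Haenszel difference.** The formula ignores the small loss from uneven strata. Simulation includes it:

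| Gap between grades | Change in variance |
|---|---|
| 0 | about +0.4% |
| 10 points | about -0.7% |
| 20 points | about -4% |
| 30 points | about -10% |

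Both estimators average 0.40. At a 20-point gap the half-width goes from 15.3 to 15.0 points.

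**6. Sensitivity to the mix.** Taking the worse side pushes people towards grade 3. With 75% at grade 3 and a 20-point gap, the formula gives 0.75 × 0.25 × 0.04 × 0.02778 = 0.000208, or 3.4%; simulation gives about 3%.

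**7. Power.** At 120 v 40 and the design rates, simulation gives about 99.5% for the unadjusted Wald test and 99.7-99.9% for a stratified Cochran-Mantel-Haenszel test. Some of that difference comes from the form of the test: it is 99.5% v 99.7% even when grade has no effect. The required sample size does not change.

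**The case against.** The strongest reply is that nothing is broken. Under randomisation the unadjusted difference is unbiased and its test is valid. The shift of up to 3.3 points is already inside the unadjusted interval and is not extra error. Power exceeds 99% at the planning rates. All of this stands. A reader might infer that the primary test is biased, has inflated type I error or is underpowered for want of adjustment; the documents support none of these.

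A reader might also infer that the plan ignores baseline grade altogether, or that stratifying is free. Neither is right. Grade enters the endpoint, the imputation model, the baseline table and a subgroup analysis, and stratifying costs about 0.4% in variance if grade is not prognostic. That it is prognostic remains an assumption. Still, the baseline and subgroup tables would only show an imbalance; they give no adjusted treatment effect.

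Two technical objections have force. First, strata of grade 2 and grade 3 alone leave out some of the analysis set: mITT requires only a non-missing baseline, and SAP Table 5-3 anticipates participants outside those grades. One sentence on placement solves this.

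Second, a Mantel-Haenszel difference need not equal the simple difference of the reported group rates, on which the hypotheses are written. The gap should be small. At exactly 3:1 within a stratum of size N, the weight is 0.75N × 0.25N / N = 0.1875N, so strata are weighted by their size. A grade-standardised difference keeps the overall rates as its target.

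Finally, the SAS code announced at the end of SAP 5.3.2 is not visible in the copy reviewed. A stratified table there cannot be ruled out, but the text describes none.

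**Conclusion.** The point holds as a modest improvement. As described, the comparison for the second hypothesis omits a baseline value that is complete for mITT and already defined per participant. Over assumed gaps of 0 to 30 points between grades, adjustment changes the variance of the difference by about +0.4% to -10%. These figures rest on 144 v 48 analysed, 80% v 40% responders, an even grade mix and an equal gap in both arms, of which only the sample sizes and overall rates come from the plan.

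At the design rates the conclusion of the trial would hardly depend on this. Precision would matter more if the true effect were smaller: exact Fisher power at 120 v 40, with treatment at 80%, is 80% for a 25-point and 62% for a 20-point difference. The priority is low and the change is optional.

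**What to change.** In SAP 5.3.2, Step 3, estimate the Mantel-Haenszel (or grade-standardised) risk difference and its standard error in each imputed dataset, stratified by worse-side baseline ALJDS grade. Pool it in Step 4 and report it with the unadjusted difference. If the sponsor prefers to keep the unadjusted test as primary, add the stratified estimate to Table 5-3 as a pre-specified sensitivity analysis.

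Define the strata as worse-side grade 2 or lower v 3 or higher, so that no mITT participant is dropped. Leave the 50% criterion for the treatment group unadjusted.

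The cost is a few lines of SAP text and a stratified table in place of a single one, settled before database lock; no new data are needed. The downsides are a negligible loss of precision if grade is not prognostic, and, with Mantel-Haenszel, an estimate that may differ slightly from the difference of the reported rates, which a footnote should explain.
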